## 7.6.25 Subject Diary Card

A diary card will be dispensed to each enrolled subject at Visit 1/Day 1. The subject will be instructed to complete the diary card to record any AEs experienced during the 2 weeks after receiving treatment. The diary card will be collected at Visit 2/Month 1.

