## 7.7.1 Visit 1/Day 1: Treatment

Visit is  $\pm 14$  days of Day 168/Month 6 telephone call for PRO 2018-03 or for subjects enrolled from PRO 2018-02, Visit 1 is Day 1.

- Obtain written informed consent and read and sign the AESI letter dated 04JUN19.
- Update the medical history and demographic information as needed from entry to Protocol PRO 2018-02 and PRO 2018-03
- Perform vital signs (temperature, heart rate, blood pressure, and respiratory rate)
- Vision evaluation (Snellen visual acuity, confrontational visual fields, ocular motility)
- Obtain/record concomitant medications/treatments

- Evaluate inclusion/exclusion criteria
- Perform urine pregnancy test for all women of childbearing potential
- Reason for study participation question
- LFGS assessment
- POL assessment
- Lip function evaluation prior to treatment administration
- Lip sensation evaluation prior to treatment administration
- Lip texture evaluation prior to treatment administration
- Lip firmness evaluation prior to treatment administration
- Lip symmetry evaluation prior to treatment administration
- Lip movement/function prior to treatment administration
- pGAI assessment prior to treatment administration
- iGAI assessment prior to treatment administration
- Swelling assessment prior to treatment administration
- Subject satisfaction with lips (VAS) prior to treatment administration
- Treatment administration waiting 15 minutes after lidocaine cream or inert cream application
- Investigator Ease of Use assessment
- Subject Pain Score immediately after treatment (VAS)
- Subject Pain Score 15 minutes after treatment (VAS)
- Vision evaluation (Snellen visual acuity, confrontational visual fields, ocular motility) 30 minutes post treatment.
- Assess AEs
- Dispense subject diary card
- Schedule next visit
- Complete CRFs

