## 7.7.3 Visit 2/Day 28 (± 2 days): Month 1 End of Study Visit

- Vision evaluation (Snellen visual acuity, confrontational visual fields, ocular motility)
- Assess concomitant medications/treatments
- LFGS assessment
- POL assessment
- Lip function evaluation
- Lip sensation evaluation
- Lip texture evaluation
- Lip firmness evaluation
- Lip symmetry evaluation
- Lip movement/function
- pGAI assessment
- iGAI assessment
- Swelling assessment
- Subject satisfaction with lips (VAS)
- Subject Pain Score (VAS)
- Assess AEs
- Treatment Question
- Collect/Review subject diary card
- Complete CRFs

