#### 7.9.5 Monitoring Adverse Events

Each subject will be monitored for the occurrence of AEs, including SAEs, immediately after treatment initiation. Each subject will be followed for safety monitoring until discharged from the study. Follow-up procedures related to pregnancy or AEs or SAEs may continue beyond the end of the study.

Subjects will be questioned and/or examined by the investigator or a qualified designee for occurrence of AEs throughout the study. The presence or absence of specific AEs should not be elicited from subjects. In addition, subjects will be instructed to record AEs on the subject diary card during the 2 weeks after treatment, and on the subject diary card dispensed at Visit 2 for the remainder of the study. Subjects having AEs will be monitored with relevant clinical assessments and laboratory tests, as determined by the investigator.

AEs, actions taken as a result of AEs, and follow-up results must be recorded on the CRF, as well as in the subject's source documentation.

For all AEs that require the subject to be withdrawn from the study and SAEs, relevant clinical assessments will be repeated as clinically appropriate until final resolution or stabilization of the event(s).

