#### WARNINGS

- Defer use of *PN40082* at specific sites in which an active inflammatory process (skin eruptions such as cysts, pimples, rashes, or hives) or infection is present until the process has been controlled.
- Injection site reactions (e.g., lip swelling, lip pain, and contusion) to *PN40082*, including short-term minor or moderate inflammatory symptoms starting shortly after treatment of lips
- PN40082 must not be implanted into blood vessels. Localized superficial necrosis and scarring may occur after injection in or near vessels, such as in the lips, nose, or glabellar area. It is thought to result from the injury, obstruction, or compromise of blood vessels.
- Delayed onset inflammatory papules have been reported following the use of dermal fillers. Inflammatory papules that may occur rarely should be considered and treated as a soft tissue infection.

- Injections of 4.0 mL or greater (upper and lower lip combined) per treatment session increases the occurrence of injection site reactions. If a volume of more than 3 mL is needed to achieve optimal correction, a follow-up treatment session is recommended.
- As with all dermal filler procedures, PN40082 should not be used in vascular rich areas.
   Use of similar products in these areas, such as glabella and nose, has resulted in cases of vascular embolization and symptoms consistent with ocular vessel occlusion, such as blindness.

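### Section 7.9.5 relies on a diary card dispensed at Visit 2 that the schedule, 7.6.25 and 7.7.3 do not provide; a site following the schedule has no diary from Day 28 to Day 168 (83% of follow-up)

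*Combined protocol and SAP*

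**What the plan says.** Section 7.9.5 (Monitoring Adverse Events) sets two diary periods. In the first, "subjects will be instructed to record AEs on the subject diary card during the 2 weeks after treatment". In the second, they record "on the subject diary card dispensed at Visit 2 for the remainder of the study". The section presents the diary as an addition to questioning or examination by study staff throughout the study, and tells staff not to ask about particular AEs.

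The operational sections describe one card only:

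- **Section 2, Schedule of Activities:** the diary row shows dispensing at Visit 1 and collection at Visit 2, and no other diary step.
- **7.6.25:** "A diary card will be dispensed to each enrolled subject at Visit 1/Day 1". The subject is to "record any AEs experienced during the 2 weeks after receiving treatment". Then: "The diary card will be collected at Visit 2/Month 1".
- **7.7.1 (Visit 1):** "Dispense subject diary card".
- **7.7.3 (Visit 2):** "Collect/Review subject diary card", with nothing dispensed.
- **7.7.4 and 7.7.5 (Day 56 and Day 168 calls):** AEs, concomitant treatments, visual and stroke symptoms, and adherence are covered. The diary is not mentioned.

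Under 7.2 a subject completes the study at the Day 168 call. Section 7.9.8 says staff review diaries whenever subjects return them, but no scheduled contact after Visit 2 could receive one.

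**The concern.** A written safety-monitoring instruction cannot be carried out from the schedule and visit lists that sites work from. Section 7.5 sends sites to Section 2 for the activities at each visit, and Section 2 has no second card. Even a site that issued one would have no instruction for reviewing it or getting it back.

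The late period matters here. Safety of repeat injection is a study objective, TEAE frequency is the safety endpoint (7.9.1), and the synopsis plans to compare AE incidence across PRO 2018-02, PRO 2018-03 and this study. Visit 2 is the last scheduled lip examination. Both Instructions for Use carry the warning "Delayed onset inflammatory papules have been reported following the use of dermal fillers". A contemporaneous diary would help to record a local event that starts and resolves between calls.

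**Working it through.** The protocol states no figure for diary coverage, so there is none to reproduce. The check is day arithmetic on the planned contacts.

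**Inputs**

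- Visit 1 card: 14 days of recording (7.6.25 and 7.9.5 agree).
- Visit 2: Day 28, ±2 days (Section 2, 7.7.3).
- Second card in 7.9.5: Visit 2 to the end of the study.
- End of follow-up: Day 168, ±7 days (7.2, 7.7.5).

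**At the planned days**

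| Quantity | Formula | Result |
|---|---|---|
| Diary cover under the schedule | 14/168 | 8.3% |
| Diary cover under 7.9.5 | (14 + (168 − 28))/168 = 154/168 | 91.7% |
| Loss due to the missing second card | (168 − 28)/168 = 140/168 | 83.3% |
| No diary under either text | (28 − 14)/168 = 14/168 | 8.3% |
| Total without a diary under the schedule | (168 − 14)/168 = 154/168 | 91.7% |

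The total splits exactly: 140 days from the contradiction plus 14 days common to both texts makes 154.

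**Over the windows, with treatment day counted as 0 or 1**

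- Loss due to the missing card: lowest (161 − 30)/161 = 131/161 = 81.4%; highest (175 − 26)/(175 − 1) = 149/174 = 85.6%.
- Total without a diary under the schedule: lowest (160 − 14)/160 = 91.2%; highest (175 − 14)/175 = 92.0%.

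**Contacts left after Visit 2.** The calls are at Day 56 and Day 168. The gap between them is 168 − 56 = 112 days. Within the windows it runs from (168 − 7) − (56 + 4) = 101 to (168 + 7) − (56 − 4) = 123 days. This gap comes from the call schedule and is the same with or without a second card. It shows how long recall must reach if there is no diary, but it does not measure the contradiction.

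**The case against.** The strongest reply is that this is one stray clause. Four places agree on a single card, 7.5 makes Section 2 the operational reference, and deleting a few words in 7.9.5 would restore consistency. That is a legitimate way to resolve it. It does not show that the text is consistent now, or that the sponsor meant to have no diary after Day 28.

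Some stronger readings are tempting, but the documents do not support them:

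- **That the contradiction costs 92% of diary cover.** It costs 83%. The rest is the two weeks before Visit 2, which 7.9.5 also leaves without a diary.
- **That late AEs go uncollected, or depend wholly on unprompted recall.** AEs and concomitant treatments are assessed at both calls, and visual and stroke symptoms are asked about directly. Section 7.7.6 allows unscheduled visits at any time, with lip assessments available. Section 7.4.3 tells subjects to contact the site about substantial swelling. The rule against asking about specific AEs applies with or without a card.
- **That sites will diverge and bias the arms.** Divergence is possible but not shown. Randomization is 1:1:1, and nothing shows that a site-level difference in diary use would favour one arm.
- **That the papule warning places such events after Day 28.** The warning calls them rare and gives no onset time.
- **That the Visit 1 card should run through to Visit 2.** Sections 7.6.25 and 7.9.5 agree on two weeks, so this would be a preference. That interval falls between the Day 14 call and a full examination at Visit 2.

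**Conclusion.** The inconsistency is real and lies in current text. Section 7.9.5 requires a card that no operational section dispenses, reviews or collects. Followed from the schedule, the study lacks the required diary for 140 of 168 days (83%; 81% to 86% over the windows and day-counting conventions), and 92% of follow-up has no diary at all.

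The consequence is limited to a supplementary record of late local events, during a period when AE collection rests on two telephone calls and any unscheduled visit and no lip examination is scheduled. The percentages assume a full 14 days of recording on the Visit 1 card and a second card kept until the Day 168 call. They measure diary time, not missed events; the documents give no basis for estimating how many events would be missed. The point should be corrected because the objective is safety of repeat injection and the correction is cheap, but it does not undermine AE collection as a whole.

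**What to change.** Decide whether a second card is intended, and make the sections agree.

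**If it is intended, as 7.9.5 now reads:** add dispensing of a second diary card at Visit 2 to Section 2 and 7.7.3; add a review of diary entries with the subject to the Day 56 and Day 168 calls (7.7.4, 7.7.5); have the card returned by mail after the last call; and revise 7.6.25 to describe both cards.

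**If it is not intended:** delete the clause in 7.9.5 and state that AEs after Day 28 are collected by telephone and at unscheduled visits only.

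The first option costs a short amendment, one card and a return envelope per subject, and a few minutes per call. It will probably record more minor AEs. Section 7.9.8 leaves it to the investigator whether a diary event that outlasts the recording period becomes an AE, so a longer diary period also changes which entries that rule reaches. The report should therefore show AEs by source (diary or call). It should also note any difference in diary period when comparing with PRO 2018-02 and PRO 2018-03. Those periods are not given in these documents, so whether a second card would help or harm comparability cannot be judged from them. The second option costs only the text change, but gives up the extra record of late events.

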#### 7.9.6 Assessment of Adverse Events

#### 7.9.6.1 Assessment of Severity

Severity of AEs will be graded according to the following definitions:

Mild: AE that was easily tolerated

Moderate: AE sufficiently discomforting to interfere with daily activity

Severe: AE that prevented normal daily activities

#### 7.9.6.2 Assessment of Causality

A medically qualified investigator must assess the relationship of any AE (including SAEs) to the use of the study device as unlikely related, possibly related, or probably related based on available information, using the following guidelines:

Unlikely related: no temporal association, or the cause of the event has been identified, or the study device cannot be implicated based on available information

Possibly related: temporal association but other etiologies are likely to be the cause; however, involvement of the study device cannot be excluded based on available information

Probably related: temporal association, other etiologies are possible, but unlikely based on available information

[figure not shown]
#### 7.9.6.3 Reference Safety Information for Assessing Expectedness of Adverse Events

For reference safety information for assessing the expectedness of an AE for the study device in this study, see Appendix 2: PN40082 Instructions for Use and Appendix 3: RV001 Instructions for Use.

## 7.9.7 Reporting Safety Observations

Any SAE, whether deemed device-related or not, must be reported to the Sponsor or designee by telephone, email, or fax as soon as possible after the investigator or coordinator has become aware of its occurrence. The investigator/coordinator must complete a Serious Adverse Event (SAE) Form and email or fax it to the Sponsor or designee along with the subject's Adverse Events Log and Concomitant Medications Log within 24 hours of notification of the event. The Sponsor will notify the FDA of device-related SAEs.

Designee and Sponsor contact details:

The investigator must be prepared to supply the medical monitor with the following information:

- 1. Investigator name and site number
- Protocol number
- 3. Subject ID (screening/randomization) number
- 4. Subject initials and date of birth

- Subject demographics
- 6. Clinical event
  - a. description
  - b. date of onset
  - c. severity
  - d. treatment (including hospitalization)
  - e. relationship to study device
  - f. action taken regarding study device
  - g. if the AE was fatal or life-threatening:
    - i. cause of death (whether or not the death was related to study device)
    - ii. autopsy findings (if available)

The Sponsor must submit a written summary of the clinical course of any life-threatening SAE and related subject information to the FDA within 7 days. Serious and unexpected AEs that are not life-threatening must be reported to the FDA within 15 calendar days. Any serious and unexpected AE (including all deaths) must also be reported to the Institutional Review Board (IRB) by the investigator according to IRB reporting requirements and documentation of this report sent to the Sponsor or designee.

The investigator must provide a follow-up written report within 5 calendar days of reporting the event to the medical monitor. The written report must contain a full description of the event and any sequelae. Subjects who have had an SAE must be followed clinically until all parameters (including laboratory) have either returned to normal or are stabilized.

#### 7.9.8 Diary Assessments

Diaries will be reviewed by the study staff each time they are returned by a subject. Entries will be reviewed for completeness and medical accuracy. Any diary events listed by the subject as persisting beyond the final recording day of the diary will be evaluated by the Investigator and may be recorded as an AE at the discretion of the Investigator.

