## 7.6.20 Swelling Assessment

Swelling will be assessed by the Blinded Evaluating Investigator at each study visit using the 5-point scale with the categories that follow. The Investigator should examine both upper and lower lip simultaneously and recall the degree of augmentation originally provided for comparison. The subject should not be specifically questioned regarding swelling but if the subject spontaneously reports it, such information can be used to assist in selection of a grade for swelling.

- 0. None No swelling noticeable. Lips appear the same as when originally augmented. Any lip enlargement is due to the implanted product only.
- 1. Minimal Slight enlargement of either lip beyond the originally provided augmentation. May or may not be noticeable to the subject but is noticeable to the investigator.
- 2. Mild Some enlargement of either lip beyond the original augmentation that is easily noticeable to the subject, but the lips do not appear abnormally large.
- 3. Moderate Significant enlargement of either lip beyond the original augmentation. Either lip appears abnormally large.
- 4. Severe Any degree of swelling that substantially interferes with lip function such as changes in speech or difficulty eating or drinking.

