## 7.9 Assessment of Safety

## 7.9.1 Safety Endpoints

Safety of the treatment with PN40082 or RV001 with topical anesthetic, or RV001 will be evaluated by the nature, severity, and frequency of treatment-emergent adverse events (TEAEs). All AEs that occur during the study will be recorded whether or not they are considered to be related to treatment. A description of the AE will be recorded with the date of onset, date of resolution, severity of the AE, relationship to the study device, action taken, and the outcome. The frequency and type of AEs will be evaluated for each group based on the previous

treatments that they received in the PRO 2018-02 and PRO 2018-03 protocols, and the difference in AEs in this protocol (PRO 2019-02) between the subjects who received injections that contained lidocaine, and the group that was treated with topical lidocaine.

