#### 7.9.3 Definitions of Terms

#### 7.9.3.1 Adverse Event

An AE is defined as any untoward medical occurrence associated with the use of a drug/device in humans, whether or not considered drug/device-related (21 Code of Federal Regulations [CFR] 312.32 (a) and 803). An AE can therefore be any unfavorable and unintended sign (including an abnormal laboratory finding, for example), symptom, or disease temporally associated with the use of a drug/device, without any judgment about causality.

Expected adverse events are defined as the events that appeared at injection site subsequent to the first injection. Expected adverse events may include but are not limited to bruising, swelling, erythema, edema, and inflammation at injection site.

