#### 8.3 Safety Analysis

Adverse events will be coded to system organ class and preferred terms using the Medical Dictionary for Regulatory Activities (MedDRA, Version 20 or higher).

Frequency and percentage of subjects reporting TEAEs will be tabulated overall and for each treatment in PRO 2019-02 by preferred terms and further by severity and relationship to study device. In summaries of severity and relationship, subjects reporting more than one event in a treatment arm that are mapped to the same preferred term will be counted only once in that treatment arm under the strongest severity and relationship, respectively. In addition, visual related TEAEs will be summarized separately by preferred term.

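### Section 7.9.8 makes it optional to record persisting diary events as AEs, while Sections 7.9.1 and 7.9.5 make AE recording mandatory (minor)

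*Combined protocol and SAP*

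**What the plan says.** Section 7.9.8 has study staff review each returned diary. For an event that the subject marks as still present when the diary ends, it says that anything lasting past "the final recording day of the diary will be evaluated by the Investigator and may be recorded as an AE at the discretion", which is the Investigator's. The evaluation is mandatory and the recording is optional.

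The general rules have no such option. Section 7.9.1 states: "All AEs that occur during the study will be recorded whether or not they are considered to be related to treatment". Section 7.9.5 states: "AEs, actions taken as a result of AEs, and follow-up results must be recorded on the CRF".

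On what the diary is for, Section 7.6.25 states: "The subject will be instructed to complete the diary card to record any AEs experienced during the 2 weeks after receiving treatment". Section 7.9.5 describes it in the same way. On what counts as an AE, Section 7.9.3.1 covers any untoward medical occurrence without a judgement on cause, and adds: "Expected adverse events may include but are not limited to bruising, swelling, erythema, edema, and inflammation at injection site".

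Section 8.3 sets the analysis: "Frequency and percentage of subjects reporting TEAEs will be tabulated overall and for each treatment in PRO 2019-02 by preferred terms".

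Two further sentences bear on how else an event might be picked up. Section 7.9.5 requires subjects to be questioned or examined for AEs throughout the study, and then says: "The presence or absence of specific AEs should not be elicited from subjects". Section 7.6.20 says of the swelling grade: "The subject should not be specifically questioned regarding swelling".

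**The concern.** The safety endpoint in Section 7.9.1 is the nature, severity and frequency of TEAEs, and repeat-injection safety is part of the study objective in Section 6. The protocol's safety analysis counts what is recorded as an AE, and it describes no separate summary of diary data. An entry that is evaluated under 7.9.8 and not recorded would therefore appear in none of the analyses the protocol describes.

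The optional rule applies to events that outlast the diary. With no stated criterion, two sites could treat the same entry differently. What is at stake is the completeness of the TEAE counts and their consistency across sites.

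**Working it through.** The plan gives no figure on this point and no arithmetic applies. The check sets the sections side by side.

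**Step 1. Do both rules cover the same event?**

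| Question | Section | Answer in the text |
|---|---|---|
| What does the subject write in the diary? | 7.6.25, 7.9.5 | AEs in the two weeks after treatment |
| What is an AE? | 7.9.3.1 | Any untoward occurrence, whatever its cause; injection-site reactions are named as expected AEs and none is exempted |
| Must an AE be recorded? | 7.9.1, 7.9.5 | Yes |
| Must a persisting diary event be recorded as an AE? | 7.9.8 | Optional, at discretion |

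Take bruising that the subject enters in the diary and marks as ongoing at its end. Under 7.9.3.1 it is an AE. Under 7.9.1 and 7.9.5 it has to be recorded. Under 7.9.8, read literally, it need not be. The two rules meet on one event.

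**Step 2. Does any other section supply a criterion?** Section 7.6.1 makes the blinded Evaluating Investigator responsible for recording AEs and judging severity and relationship, but sets no threshold for recording. Section 7.9.6 defines severity and causality grades, and neither works as a filter on recording. Section 8.3 starts from recorded TEAEs. No duration, severity or other criterion for leaving out a diary event was found.

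**Step 3. When would a count in the 8.3 table actually change?** Section 8.3 counts subjects with a preferred term. A subject is lost from a term only if all of the following hold:

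1. The subject wrote the event in the diary and it was still present at the diary's end.
2. It was not already recorded from the Day 3 or Day 14 call.
3. It was neither reported nor observed at the Visit 2 AE assessment, and was not reported on Day 56 or Day 168.
4. The Investigator used the 7.9.8 discretion not to record it.
5. No other event of that subject under the same preferred term was recorded.

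The documents give no frequency for any of these, so no change in a TEAE percentage can be calculated.

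**Step 4. The separate diary mismatch.** Section 7.9.5 relies on a second diary card given out at Visit 2 and used to the end of the study. The Section 2 schedule, 7.6.25 and 7.7.3 only collect a diary at Visit 2. The contacts after that (7.7.4 and 7.7.5) are telephone calls with no diary return. A side effect is that the last recording day in 7.9.8 has two possible meanings: the end of the two-week card, or the end of the study.

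**The case against.** The strongest reply is that 7.9.8 is loosely worded and does not license omissions. Diary entries are lay reports. Someone has to decide whether each one is an untoward medical occurrence, and 7.9.8 puts a mandatory evaluation before the discretion. Read together with 7.9.1 and 7.9.5, optional recording can simply mean recording if the entry is judged to be an AE. This reading is reasonable and may be what the sponsor intends. It weakens the conflict but does not remove it, because 7.9.8 does not say that the discretion stops there.

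The second reply is that other routes catch these events, and most of this stands. General AE questioning is required throughout the study; only prompting for specific AEs is barred. Visit 2 pairs the AE assessment with review of the diary, and the evaluator examines the lips at the same visit. An event still present when the diary ends began within two weeks of treatment, so the Day 3 and Day 14 calls would often have recorded it already.

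A reader might infer from the bar on prompting, and from the instruction in 7.6.20, that staff cannot follow up a diary entry. The documents do not support that. An entry is already volunteered by the subject, and neither sentence clearly forbids asking about it. Section 7.6.20 concerns only the swelling grade, and it allows spontaneous reports to inform that grade.

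A reader might also take the delay in collecting the diary as a measure of the problem. The two-week diary ends on Day 14 or 15, depending on whether Day 1 is counted, and Visit 2 falls on Day 26 to 30. The gap is therefore 26 − 15 = 11 to 30 − 14 = 16 days for visits within the window. This describes the collection schedule. It would be the same if 7.9.8 made recording mandatory, so it says nothing about how many events are lost.

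**Conclusion.** The conflict in wording is real and the point is minor. Read literally, 7.9.8 permits an AE entered in the diary to be left out of the TEAE tables, against 7.9.1 and 7.9.5. The practical exposure is limited to diary entries not captured at any other contact. Its size cannot be derived.

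Two stronger conclusions are tempting and are not supported. One is that the protocol sets out to drop confirmed AEs; the discretion can equally be read as a judgement on the definition. The other is that the arms would be biased against each other. Nothing in the documents makes the discretion depend on treatment, and 7.6.1 gives AE recording to the blinded evaluator. The point concerns completeness and consistency of counts only.

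It rests on two assumptions: that sites would follow 7.9.8 as written, and that the separate SAP promised in Section 8, which is not part of the document reviewed, adds no rule for diary events.

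The reference in 7.9.5 to a diary given out at Visit 2 is a separate documentation error. It stands on its own and does not add weight to the point on discretion.

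**What to change.** Replace the last sentence of 7.9.8 with wording such as: *Every diary entry that meets the definition of an AE in Section 7.9.3.1 is recorded as an AE on the CRF. Investigator judgement is limited to whether the definition is met, and to severity and causality.* If the sponsor already intends the narrower reading, this only states it.

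Separately, reconcile 7.9.5 with Section 2, 7.6.25 and 7.7.3. Either delete the diary given out at Visit 2, or schedule its dispensing and its return.

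The cost is one sentence in 7.9.8, one correction in 7.9.5 (or matching entries in Section 2, 7.6.25 and 7.7.3), and a short reminder to sites. There may be a few more AE lines to enter and code, and reported TEAE percentages may be slightly higher. No extra subjects are needed, and no extra visits if the Visit 2 diary is deleted.
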